### **Inclusion criteria**

To be included in the longitudinal cohort study, participant must be between the age range six months to 15 years and be resident in the study area for the period of the study. Willingness to participate will be proven by a completed and signed consent form from the parent or guardian of each child. All other community members will be engaged in the survey studies.

### **Exclusion criteria**

If an individual intents to stay less than one year in the study site or would be absent at some time because he/she is schooling in a boarding school or has a life threatening illness (excluding malaria). However, all individuals including those with clinical malaria signs who are present during surveys will be tested and if confirmed to carry the parasite will be treated.

### **Data collection**

Following consent, blood will be drawn from a finger prick. All participants will be tested for the presence of malaria parasites using RDTs. Additionally, blood will be collected on filter paper to enable molecular characterization in case treatment failure is observed in a given patients as explained above. All samples will be stored at NMIMR. To test for anaemia (for children in the cohort study only), a portable automated Hemocue photometer will be used to determine the concentration of Haemoglobin. Anaemia in this study is defined as Hb levels less than 10g/dl. Children with severe anaemia (Hb less than 7g/dl) will be referred to the Pakro Health Centre for follow up. **At evaluation, family members will be asked questions on how much they used to spend on malaria before the intervention and how much they have spent after. Malaria case management records before and after the intervention will be consulted, firstly to determine the change in prevalence and also for cost benefit analysis purposes.**

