### **Study Design:**

This is an Implementation Research (IR) with a longitudinal cohort design to be undertaken within a two year frame work. The interventions are designed to compare the baseline to evaluation findings following the modified protocol of (Ahorlu et al., 2011). **There are two components to this implementation study a). The longitudinal (cohort) study: This is basically the prevalence surveys to be conducted with the selected cohort of children 6 months to 15 years – at baseline and before each of the subsequent MTTT rounds. b). The Survey involves using structured questionnaire to interview caretakers of children under five to solicit their views on the implementation process perceived benefits and challenges etc.** Though the target group is children from 6 months to 15 years of age, all parasitised adults will be cleared of the parasite during the interventions as well to reduce the parasite reservoirs. **Prevalence of malaria**

**trends in cohort group over the study period will reveal the effect of MTTT scale-up on the children 6month to 15 years.** Between interventions, the teams will conduct homes-based management of malaria for all febrile cases confirmed to be positive for malaria parasites. The challenges faced by the implementation team will be documented at every stage and discussed with all the stakeholders at every stage of the implementation.

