## **Methodology**

### **Study Area**

Pakro is one of five sub-districts in the Akwapim south district health directorate (DHD) in the Eastern region of Ghana (DHD, 2014). The Akwapim south district lies within the semi-equatorial climatic region, and experiences two rainfall seasons in a year, with an average rainfall of 125cm to 200cm. The first rainy season begins from May to June with the heaviest rainfall in June, whilst the second rainy season begins from September to October. According to the Ghana Statistical Service (GSS), the average household size in the Akwapim South district is estimated to be 4.0 whilst the average number of households per house or compound is estimated to be 1.6 (GSS, 2010). The Pakro sub-district has an estimated population of 7,889, and is bounded to the east by Akwapim North district; to the north by Ayensuano district; and to the west by Nsawam Adoagyiri Municipality. The sub-district is made up of 22 communities, and has 3 health care facilities (1 Health Centre and 2 Community-Based Health Planning Service (CHPS) compounds) (DHD, 2014). Due to limited resources, only seven communities will be selected for this study. This include Abeasi Newsite, Fante Town, Zongo (Adjenase/Kweitey), Piem/odumsisi, Adesa Latebibio, Sacchi/Tabankro and Odum Tokuro. These are communities with a relatively high population density. The Pakro Health Centre is one of thirty sentinel sites monitoring malaria prevalence in the country coordinated by the Noguchi Memorial Institute for Medical Research (NMIMR). Malaria parasite positivity rate was estimated to be 45.7% in 2014 (DHD, 2014). In the same year anaemia among pregnant women at 36 weeks of gestation was 21% (DHD, 2014).

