### **Study participants**

Community entry activities to sensitise the chiefs and the general population will be conducted at the beginning of the study through meetings and durbars (Ansah et al., 2015; Ahorlu, et al., 2009). Once the community leaders and the population have accepted the project, the household will be numbered and participants per household will be registered during a household census. All households will be given a unique identification code. Each individual within the household will be assigned a code that links them to a particular household and community. After obtaining consent from the household heads, the children will be enrolled but individual assent and consent will be obtained from the other adolescents and adults in the household. **A cohort of 460 children age 6 months to 15 years will be selected and enrolled into the longitudinal study which will consist of prevalence surveys undertaken before each MTTT. Caregivers of the children in the cohort will be enrolled for the community surveys using questionnaires. In this implementation research the entire population of the seven selected communities will be tested, treated and tracked. This is intended to clear the parasite pool in the community.**

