### ***Work Plan***

Outcome	Measure	Time frame	Mile stone
Proposal development	Draft proposal is available	Aug –Oct 2016	Submitted to the STC/IRB

Ethical Clearance	Ethical clearance is obtained	Nov - Jan 2016	clearance is available
Administrative/ Ethical clearance from Ghana Health Service	Administrative and GHS-ERC clearance are obtained	Feb – April 2016	Clearance is available
Communities/durbar	Meeting/durbars held	Nov 2016	Project is accepted by the community
Mapping of households /census of participants	All households are numbered and individual identified	Nov 2016	Each households has a number
Planning for data collection	Consumables are prepared, RDTs are bought	Dec - Jan 2016	All necessary equipment and consumable are available in the field
Primary	The prevalence of asymptomatic malaria parasitaemia among afebrile children aged 6 months to 15 years and adults will be known in the Pakro sub district.	Two years  1st survey Apr - Jul 2017	Reports, Publications, Presentations at conferences and workshop demonstrating the effect of the intervention on malaria prevalence in Pakro sub district in the Eastern Region of Ghana
Secondary	Reduce the burden of malaria in the participating communities.	2nd survey Aug - Oct 2017	
	Challenges that hinder the scale up of mass testing, treatment and tracking of malaria in Ghana are documented.	3rd survey Nov - Jan 2017	
	The cost benefit analysis of the scaling up MTTT intervention in the communities will be known.	4th survey Feb - May 2018	
	Options for policy are proposed.	5th survey Jun - Sep 2018  6th survey Nov 2018 - Feb 2019	
Evaluation	What is the effect of the intervention? What is the prevalence? What are the lessons learned for scaling up.	Jan - July 2019	Report publication

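### Household malaria spending before the intervention is described as asked only at evaluation, about 17 to 28 months after the 1st survey, although a caregiver questionnaire is already budgeted before round 1

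*Protocol*

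**What the plan says.** The Data collection section describes a single household-spending enquiry: "At evaluation, family members will be asked questions on how much they used to spend on malaria before the intervention", followed in the same sentence by "how much they have spent after". That text gives no reference period for either amount. The next sentence turns to malaria case management records before and after the intervention, which are to be consulted "firstly to determine the change in prevalence and also for cost benefit analysis purposes".

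The Work Plan dates the 1st survey April to July 2017, the 6th survey November 2018 to February 2019, and evaluation January to July 2019. The milestone in the evaluation row is "Report publication".

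A questionnaire is planned as well. Under Study participants, "Caregivers of the children in the cohort will be enrolled for the community surveys using questionnaires". The budget explanation for the longitudinal cohort study funds the PI and a research assistant for one week in the community ahead of every intervention to administer it, six times in all, so the first falls before round 1. Its content is described as malaria treatment, prevention and control practices (Questionnaire/Focus group Discussion). Study Design describes the survey as one to "interview caretakers of children under five to solicit their views on the implementation process perceived benefits and challenges etc". Neither description mentions spending.

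The Benefits section states as a fact that the study will lower what households spend on malaria. Data Management and Analysis defines the cost-benefit analysis by NMCP expenditure.

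**The concern.** A household's spending before the intervention can be asked about directly only until round 1 starts in its community. After that it can only be recalled. As described, respondents give the earlier amount more than a year later, after rounds of free testing and treatment, and in the same interview as the later amount. Either figure may be shaped by memory or by what respondents know of the programme. No later analysis can recover a baseline that was not collected, so this has to be settled in data collection.

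At stake is the credibility of one side comparison. It matters because nothing else described in the protocol measures the household saving that Benefits presents as an outcome of the study.

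**Working it through.** The protocol gives no figure of its own to reproduce on this point. The check is a calendar calculation from the Work Plan, followed by a comparison of sections.

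**Step 1: interval from the 1st survey to the retrospective question.** Months are days divided by 30.4375.

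- Shortest within the evaluation row: 31 July 2017 to 1 January 2019 = 519 days; 519 / 30.4375 = 17.1 months.
- Longest: 1 April 2017 to 31 July 2019 = 851 days; 851 / 30.4375 = 28.0 months. This is a worst case, because the evaluation row also covers reporting.
- If the question were asked in the last funded questionnaire week, before round 6: 31 July 2017 to about 1 November 2018 = 458 days; 458 / 30.4375 = 15.0 months.

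The pre-intervention period lies before the 1st survey, so the true recall distance is at least as long as these intervals.

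**Step 2: is there an earlier opportunity?** Yes. The longitudinal cohort budget places a questionnaire week ahead of each of the six interventions. The Budget table names the respondents as parents or guardians of enrolled children. Only the budget explanation gives this timing; the Study participants section enrols the caregivers without dating the interview.

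**Step 3: what depends on the spending question?** Set side by side:

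- Benefits asserts lower household spending, and the Data collection question is the only described measurement that bears on it.
- Data Management and Analysis bases the cost-benefit analysis on NMCP expenditure, and Data collection ties cost-benefit purposes to case management records. Neither is described as using recalled household spending.
- Prevalence rests on rapid tests and admissions on facility records. Neither uses the question.

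**Step 4: size of the bias.** The document gives no spending level and no recall-error figure. Neither the size nor the direction can be derived.

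**The case against.** The strongest reply is that the data collection instruments are listed as attached and are not shown. A reference period is a matter of item wording and would normally sit there, and a baseline spending item could sit there too. The descriptions of the questionnaire are not exhaustive. This stands in part: a reader might infer that no baseline item and no recall window exist, and the document does not support that. What remains is that the protocol text itself places the question about earlier spending at evaluation.

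It can also be said that no objective or stated analysis uses household spending, and that Benefits is an ethics statement rather than an endpoint. That stands, and it limits the point to an ancillary comparison. A reader might infer that the cost-benefit analysis is undermined. It is not, because it is defined by NMCP costs.

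A third reply is that 17 months is not a firm minimum, since the 6th survey overlaps the evaluation row. That is correct; the interval could be about 15 months. The shorter figure does not change the conclusion.

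Finally, one might want evaluation interviews matched by season to the 1st survey. The rainy seasons are described as follows: "The first rainy season begins from May to June with the heaviest rainfall in June" and "the second rainy season begins from September to October". Interviews in January to March 2019 would fall at a different time of year from a baseline in April to July. However, the costed trips are 6 interventions, 18 monitoring visits and 1 census, and monitoring is costed within 24 months, which from April 2017 ends about March 2019. No questionnaire visit in April to July 2019 is shown, so matched interviews cannot be assumed to be free.

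**Conclusion.** The point holds in a limited form and is an optional improvement. As the protocol text describes it, the earlier amount is recalled about 17 to 28 months after the 1st survey (about 15 if asked before round 6), although a funded interview with caregivers takes place before round 1. The household-spending comparison is therefore exposed to avoidable recall bias.

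A reader might go further and infer that household savings would be overstated. The document gives no basis for a direction. The prevalence, admissions and NMCP cost results stand apart from this.

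The conclusion assumes that the Work Plan dates are kept, that the questionnaire is administered before round 1 as budgeted, and that the unseen instruments do not already contain a baseline spending item.

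**What to change.** Add a few household malaria-spending items, with a stated reference period, to the caregiver questionnaire given before the first intervention. At the evaluation interview, ask the same caregivers the same items over the same period. Because Study Design, Study participants and Data collection name different respondents (caretakers of under-fives, caregivers of cohort children, family members), say that the caregivers of cohort children are meant. Base the before-after comparison on the two values and keep the retrospective question only as a check. If the attached instruments already hold a baseline item, the change is only to align the Data collection text with it. If the evaluation interview falls in a different season from the baseline, report this as a limitation.

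The new burden falls on the week before round 1, since spending is already to be asked at evaluation. As an upper limit, with one interview per cohort child, two interviewers and seven days, the load is 460 / (2 × 7) = 32.9 interviews per person per day. If the items take 1 to 3 minutes each (an assumption), that adds about 33 to 99 minutes per interviewer per day. Caregivers with several cohort children reduce this, and a random subset of caregivers could be asked if the week is too tight. No visit is added before round 1.

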### **Timely treatment of suspected febrile malaria case in the community**

In order to render operational the home-based management component of the project, two volunteers will be selected from each community and trained on home-based management of malaria and be provided with the protocol, RDTs and ACTs. **The interventions will be carried out quarterly (see the timetable).** Between one MTTT intervention and the next trained community members will provide prompt home-based treatment for children and adults reporting signs and symptoms of malaria and confirmed to be carrying the parasite using RDTs. This will be done using national malaria management protocol. There will be monthly visits by the research team to supervise the community volunteers involved in home-based

management to ensure that the protocol is being respected as well as replenish their stocks. There is a need to visit the health facilities that service the community to enable tracking and linking of medical records with study participants (a master student is required for this component). The investigators hypothesize that a reduction in parasite load in the community will consequently lead to a reduction in the number of hospital malaria related consultations and admissions paving the way for pre-elimination. This will be realised by comparing baseline hospital malaria admission data to evaluation data. **MTTT has already been adopted by the NMCP as one of the control and elimination activities and the investigators are anticipating its being scaled-up in the country, and therefore documenting its implementation challenges will inform the decision in the future.**

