### ***Conflict of Interest***

**The PI and co-PIs declare no conflict of interest in the execution of this project.**

### ***Benefits***

All confirmed malaria parasitaemia cases will be treated for free. Continuous monitoring and treatment of confirmed cases will improve the health of residents. The study will reduce household spending on malaria thereby free some funds to be spent on other household items. This project could reduce the malaria related burden in the implementing communities.

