### RDTs

#### *Survey*

A pack contains 40 RDTs. Given that the target population of the targeted communities is 4,500 people, it is important to buy 5000 RDTs for each intervention (i.e. 125 packs). This is because some of the RDTs could give inconclusive results which will require that the process be repeated. Each RDT pack of 40 cost \$25.15. Each RDT cost \$0.63. The total cost for RDTs for the 6 surveys is given by  $(\$0.63 \times 5000 \times 6)$  of **\$18,900**. Pakro Health Centre is a sentinel site for monitoring malaria prevention which is being let by the Epidemiology Department of Noguchi. In this light, the RDTs and Antimalarials will be obtained from the National Malaria Control Programme, so the estimated cost which was based on RDT and drugs has been dropped.

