### **Incentive to children enrolled in the study**

It is estimated that children under five years make up 30% of the population of Pakro sub district. This gives  $(0.3 \times 4500)$  1350 children. We will be giving a token of a biscuit pack worth \$0.25 to each under five child tested. The adults will not be included in this package as the free treatment is already a good incentive for the community. Cost of incentives for children  $\$0.25 \times 1350 = \$337.5$  per survey. The 6 surveys will cost  $\$337.5 \times 6 = \$2,025$

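### Household malaria spending is compared before and after while the project treats confirmed cases free, so the difference cannot be read as a saving due to less malaria

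*Protocol*

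**What the plan says.** Under Data collection, family members are to be asked at evaluation "how much they used to spend on malaria before the intervention and how much they have spent after". The section describes amounts only. It goes on to say that malaria case management records from before and after will be consulted, partly for the cost-benefit analysis, which is a specific objective and an expected result of the study.

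Care is free to households during the study. The Benefits section says "All confirmed malaria parasitaemia cases will be treated for free", and the budget note on incentives for children says "the free treatment is already a good incentive for the community". Two volunteers per community are to be "trained on home-based management of malaria and be provided with the protocol, RDTs and ACTs" (Timely treatment of suspected febrile malaria case in the community). The same section adds: "Between one MTTT intervention and the next trained community members will provide prompt home-based treatment for children and adults". The budget note on survey RDTs says "the RDTs and Antimalarials will be obtained from the National Malaria Control Programme". Free treatment is stated outright. That tests are also free is implied by the supply arrangements but not said in so many words.

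The Benefits section also says "The study will reduce household spending on malaria thereby free some funds to be spent on other household items". On design, the protocol says "The interventions are designed to compare the baseline to evaluation findings" (Study Design), and no concurrent control is described.

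**The concern.** What a household spends on malaria is the number of episodes multiplied by what it pays for each. The intervention aims to reduce the first factor. It also directly reduces the second, because the project bears the cost of the care it delivers. A before-after difference in the total does not show which factor moved. This is separate from recall error and would remain if every family remembered its spending perfectly.

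At stake is the meaning of the household figure within the cost-benefit objective. If it were read as money saved because there is less malaria, part or all of it could be cost that has only moved from the family to the programme. The protocol expects its findings to inform decisions on national scale-up, where that distinction matters.

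**Working it through.** **The protocol's own figure.** No size, power or expected change is attached to the spending comparison, so there is nothing to reproduce for it directly. The nearest figure is the budget for home-treated cases: 7 communities × 5 cases × 24 months = 840, which reproduces. This planning number is flat over two years. Even if it never falls, each of those cases that a family would once have paid for no longer costs it anything for drugs.

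**Timing.** The Work Plan puts evaluation in January to July 2019, overlapping the sixth survey (November 2018 to February 2019). Home-based testing and treatment are budgeted for all 24 months. No later period at ordinary prices is described, so on its natural reading the later amount covers the period of free care.

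**Formula.** Set former spending to 1 and define:
- *b*: malaria episodes after, divided by episodes before;
- *c*: share of former spending that went on tests and drugs;
- *s*: share of that care the project now supplies free.

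Assume other costs per episode, such as transport, are unchanged. Then

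spending after / before = *b*(1 − *cs*), and relative fall = 1 − *b*(1 − *cs*).

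The documents give neither *c* nor *s*, so a range is needed.

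**Malaria unchanged (*b* = 1).** The fall is *c* × *s*:

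| *c* | *s* = 0.25 | *s* = 0.5 | *s* = 0.75 | *s* = 1 |
|---|---|---|---|---|
| 0 | 0% | 0% | 0% | 0% |
| 0.25 | 6% | 13% | 19% | 25% |
| 0.5 | 13% | 25% | 38% | 50% |
| 0.75 | 19% | 38% | 56% | 75% |
| 1 | 25% | 50% | 75% | 100% |

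**Malaria rising.** Spending is flat when *b* = 1/(1 − *cs*). At *c* = *s* = 0.5 this is 1/0.75 = 1.33, so malaria could rise by up to a third before household spending stopped falling.

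**Malaria falling by a fifth (*b* = 0.8, *c* = *s* = 0.5).** The total fall is 1 − 0.8 × 0.75 = 40%. It splits exactly into two parts, because 1 − *b*(1 − *cs*) = (1 − *b*) + *bcs*:
- fewer episodes at the old cost: 1 − 0.8 = 20%;
- change of payer on the remaining episodes: 0.8 × 0.25 = 20%.

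Here the raw difference is twice the part due to less malaria. Knowing episodes and amounts paid in both periods is enough to make this split.

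**The case against.** There are four objections of substance.

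*The protocol does not claim that lower spending proves less malaria.* This stands. A reader might infer such a claim from the Benefits section, but that passage states free treatment first and then a fall in household spending. This is a true benefit to participants whatever its mechanism, and it needs no rewording. Data Management and Analysis judges the effect on malaria by baseline against evaluation prevalence.

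*The written cost-benefit analysis does not use household spending.* This also stands. It compares what the national programme spent in earlier years with what it would spend under MTTT. A reader might infer that a transfer is already being booked as a saving, but the text does not say so. If household figures were added, the programme's spending would sit on the other side and the transfer would net out. The question of how much of the household figure is due to less malaria would remain. The protocol does not say how the household figures will be used, and an analysis plan not shown may do so.

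*Other data may help.* A reader might conclude that nothing collected could separate payer from disease. That cannot be shown. The data collection instruments are listed as attached but are not in the text, and the questionnaire is said to cover malaria treatment. Case management records and health centre registers also give case volumes. As described, those records do not give the price a household paid per episode.

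*The size is unknown.* This stands. If tests and drugs were already free to these families, the effect shrinks towards zero. A reader might instead size it from the budget: RDTs of $19,958.40 plus treatment of $6,690 make $26,648.40, or $23.69 for each of 4,500/4.0 = 1,125 households. That does not measure displaced spending. The survey rounds account for $18,900 + $5,850 = $24,750, or 93%, chiefly mass testing that families would not otherwise have bought. The home-based lines come to $1,058.40 + $840 = $1,898.40, about $1.69 per household. Both are programme unit costs, so neither is an estimate of the bias.

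**Conclusion.** The concern holds in a limited form. The before-after difference in total household spending combines a change of payer with any change in malaria and cannot be read as a saving due to reduced malaria. With malaria constant, the fall equals the share of former spending now supplied free: 6% to 100% for *c* and *s* each between 0.25 and 1, and nil if families previously paid nothing for this care or use none of the free supply. The range is assumed, and it rests on spending being proportional to episodes and on costs other than tests and drugs being unchanged. The direction of the effect follows from free treatment together with the absence of a described control, provided families previously paid something. The matter concerns a secondary economic outcome and does not bear on the prevalence comparison.

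**What to change.** In Data collection, unless the attached questionnaire already does this, have it record for both periods the number of malaria episodes in the household, where each was treated, and the amount paid.

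Report the household result in two lines:
- (a) the change in episodes times the pre-intervention cost per paid episode, scaled by the share of earlier episodes that were paid for so that the lines add up;
- (b) the cost shifted from household to programme.

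State that line (b) is not a net gain unless the corresponding programme cost is counted on the other side.

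The cost is a few more items in a questionnaire already planned and a little more analysis. The downside is that the saving attributable to reduced malaria will probably be smaller than the raw difference. If the questionnaire already holds these items, only the analysis wording needs to change.
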